10.2 Serious Adverse Events

A serious adverse event (SAE) is any untoward medical occurrence that at any dose meets 1 or more of the following criteria:

- Is fatal
- Is life threatening
 - Note: Life-threatening refers to an event that places the patient at immediate risk of death. This definition does not include a reaction that, had it occurred in a more severe form, might have caused death
- Requires or prolongs in-patient hospitalization

Page 45

- Results in persistent or significant disability or incapacity
- Is a congenital anomaly or birth defect, that is, an AE that occurs in the child or fetus of a patient exposed to IP prior to conception or during pregnancy
- Is an important medical event or reaction.

The reporting period for SAEs begins after informed consent is obtained and continues through 4 weeks after the last visit.

Any SAE, whether or not considered related to study drug, must be reported within 24 hours of knowledge of the event by forwarding (fax, email) the study-specific SAE Report Form to Catalyst and CRO. The Investigator should not wait to collect information that fully documents the SAE before notifying Catalyst. As additional information becomes available, including but not limited to the outcome of the SAE and any medication or other therapeutic measures used to treat the event, it must be reported within 24 hours in a follow-up report.

The Investigator should follow all unresolved SAEs until the events are resolved or stabilized, the patient is lost to follow-up, or it has been determined that the study treatment or participation is not the cause of the AE. Resolution of AEs (with dates) should be documented in the CRF and in the patient's medical record.

For some SAEs, Catalyst and/or designee may follow up by telephone, fax, email, and/or a monitoring visit to obtain additional case details deemed necessary to appropriately evaluate the SAE report (e.g. hospital discharge summary, consultant report, autopsy report).

At the last scheduled visit, the Investigator should instruct each patient to report any subsequent SAEs that the patient's personal physician(s) believes might be related to prior study treatment.

The Investigator should notify Catalyst and CRO of any death or SAE occurring at any time after a patient has discontinued, or terminated study participation, if felt to be related to prior study treatment. Catalyst should also be notified if the Investigator should become aware of the development of cancer, or of a congenital anomaly, in a subsequently conceived offspring of a patient that participated in this study.

Reporting of SAEs to the IEC will be done in compliance with the standard operating procedures and policies of the IEC and with applicable regulatory requirements. Adequate documentation must be provided showing that the IEC was properly and promptly notified as required.

Page 46

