- ^f IP will be administered by the clinic staff during in-clinic visit so assessments can be timed according to IP administration.
- ^g Patients will be provided blinded packages containing amifampridine or placebo depending on their randomized sequence of treatment. Collect all open-label medication.
- ^h SAE reporting commences when informed consent is signed. Non-serious adverse event reporting commences on Day 1 of run-in (Section 10).

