10.1 Adverse Events

For this protocol, a reportable AE is any untoward medical occurrence (e.g. sign, symptom, illness, disease or injury) in a patient administered the IP or other protocol-imposed intervention, regardless of attribution. This includes:

- AEs not previously observed in the patient that emerge during the study.
- Pre-existing medical conditions judged by the Investigator to have worsened in severity or frequency or changed in character during the study.
- Complications that occur as a result of non-drug protocol-imposed interventions.

An adverse drug reaction is any AE for which there is a reasonable possibility that the IP caused the AE. "Reasonable possibility" means there is evidence to suggest a causal relationship between the IP and the AE.

Whenever possible, it is preferable to record a diagnosis as the AE term rather than a series of terms relating to a diagnosis.

The study period during which all non-serious AEs will be reported begins after the first administration of study drug through the termination visit or at the early termination visit. After informed consent but prior to initiation of study treatment, only SAEs associated with any protocol-imposed interventions will be reported. The criteria for determining, and the reporting of SAEs is provided in Section 10.2 Serious Adverse Events

The Investigator should follow all unresolved AEs until the events are resolved or stabilized, the patient is lost to follow-up, or it has been determined that the study treatment or participation is not the cause of the AE. Resolution of AEs (with dates) should be documented on the appropriate CRF page(s) and in the patient's medical record.

The Investigator responsible for the care of the patient or qualified designee will assess AEs for severity, relationship to IP, and seriousness (refer to Section 10.2 Serious Adverse Events for SAE definition). Severity (as in mild, moderate or severe headache) is not equivalent to seriousness, which is based on patient/event outcome or action criteria usually associated with events that pose a threat to a patient's life or functioning. Seriousness (not severity) serves as a guide for defining regulatory reporting obligations.

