12.4 Period 2, Days 21 and 28 (or Early Termination Visit)

Patients will report to the study site on Days 21 and 28 (± 1 day) and have the assessments/procedures listed below completed. Study personnel will administer a dose of the patient's blinded medication at the clinic on Days 21 and 28, so assessments can be

performed according to the specified times in relation to the time of dose administration. The medication administered by study personnel should be the same as what the patient has been taking for Period 2. If the patient is taking study medication 3 or 4 times a day, the visit needs to be arranged such that one of the doses is administered by the study site personnel.

- Assessment of AEs/SAEs;
- Complete physical exam (Day 28 only);
- Vital signs (seated position), including SBP, DBP, heart rate, respiration, and body temperature;
- 12-lead ECG (Day 28 only);
- Clinical laboratory tests (Day 28 only);
- Urine pregnancy test in females of childbearing potential (Day 28 only);
- Concomitant medications;
- Collect patient Drug Dosing Diary and perform IP accountability (a new Drug Dosing Diary is given to the patient on Day 21);
- Efficacy assessments following in-clinic dose of double-blind medication as listed below:

Order of Assessment at Each Study Visit (when applicable)	Start Time After Dose (+ 10 minutes unless otherwise specified)
HFSME	45 minutes
6-minute walk test	After HFSME
Time to rise from floor	After 6-minute walk
Time to rise from chair	After rise from floor
Time to climb 4 stairs	After rise from chair
Time to walk 10 meters	After climb stairs
Quality of Life Assessment	After 10-meters walk

• INQoL for neuromuscular disease or the PEDSQLTM assessments will be completed for adult or pediatric patients, respectively after the six other assessments have been made.

Page 53

On Day 28, all Period 2 study medication should be collected after the assessments have been performed. This represents the end of the study.

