#### 10.12.1Adverse Events

For this protocol, a reportable AE is any untoward medical occurrence (e.g. sign, symptom, illness, disease or injury) in a patient administered the IP or other protocol-imposed intervention, regardless of attribution. This includes:

- AEs not previously observed in the patient that emerge during the study.
- Pre-existing medical conditions judged by the Investigator to have worsened in severity or frequency or changed in character during the study.
- Complications that occur as a result of non-drug protocol-imposed interventions.

An adverse drug reaction is any AE for which there is a reasonable possibility that the IP caused the AE. "Reasonable possibility" means there is evidence to suggest a causal relationship between the IP and the AE.

Whenever possible, it is preferable to record a diagnosis as the AE term rather than a series of terms relating to a diagnosis.

The study period during which all non-serious AEs will be reported begins after the first administration of study drug through the termination visit or at the early termination visit. After informed consent but prior to initiation of study treatment, only SAEs associated with any protocolimposed interventions will be reported. The criteria for determining, and the reporting of SAEs is provided in Protocol Section 10.2.

The Investigator should follow all unresolved AEs until the events are resolved or stabilized, the patient is lost to follow-up, or it has been determined that the study treatment or participation is not the cause of the AE. Resolution of AEs (with dates) should be documented on the appropriate CRF page(s) and in the patient's medical record.

The Investigator responsible for the care of the patient or qualified designee will assess AEs for severity, relationship to IP, and seriousness (refer to Protocol Section 10.2 for SAE definition). Severity (as in mild, moderate or severe headache) is not equivalent to seriousness, which is based on patient/event outcome or action criteria usually associated with events that pose a threat to a patient's life or functioning. Seriousness (not severity) serves as a guide for defining regulatory reporting obligations.

The Investigator will determine the severity of each AE using grades defined in Table 1 (the event will be recorded on the source documents and AE CRF). Events that are Grades 4 and 5 are serious events and require completion of both an SAE form and AE CRF.

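### Three narrower reporting rules undercut the all-cause SAE window in Protocol Section 10.2, so SAEs in the 4 weeks after the last visit can be missed

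*Protocol*

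**What the plan says.** Protocol Section 10.2 sets the window: "The reporting period for SAEs begins after informed consent is obtained and continues through 4 weeks after the last visit". It also sets the scope: "Any SAE, whether or not considered related to study drug, must be reported within 24 hours of knowledge of the event". Table 1, footnote h, agrees on the start and adds no condition on cause: "SAE reporting commences when informed consent is signed".

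Three rules are narrower.

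- **Before first dose.** Protocol Section 10.1: "After informed consent but prior to initiation of study treatment, only SAEs associated with any protocol-imposed interventions will be reported". SAP Section 10.12.1 carries the same sentence, beginning "After informed consent but prior to initiation of study treatment, only SAEs associated with any".
- **Exit instruction to the patient.** Section 10.2 gives the Investigator this task for the final planned visit: "instruct each patient to report any subsequent SAEs that the patient's personal physician(s) believes might be related to prior study treatment".
- **Investigator's later notification.** Near its end, Section 10.2 asks the Investigator to notify the sponsor and CRO of deaths and SAEs that occur after a patient has left or finished the study, on condition that they are thought to be due to the study treatment. It gives no starting point other than the end of participation.

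On contact, Section 12.4 says of Day 28: "This represents the end of the study". Table 1 has no later column, and Section 12 describes no later call.

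**The concern.** The plan promises all-cause collection of SAEs for 4 weeks after the last visit, but the two rules that operate in that period ask only for events presumed related. The first person to judge cause would be the patient's own physician, who may not know about the trial drug. Section 10.1 gives that judgement to the Investigator or a qualified designee. An event that no one links to the drug may therefore never reach the person who is meant to assess it.

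Safety and tolerability is a primary objective, and about 12 patients are to be randomized, so a single unreported SAE would matter to the safety account. The Safety Population (Protocol Section 14.2, SAP Section 10.1) also includes run-in patients who are never randomized. No contact is scheduled for them after they leave either.

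Before first dose the problem is different. Two sections give a site opposite answers about the same event.

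**Working it through.** The plan gives no figure to reproduce, so the check is to set the rules side by side and then count days.

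**Step 1. Apply each rule to the same event.**

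| SAE not thought related to drug or procedures | General rule in 10.2 | Narrower rule |
|---|---|---|
| Between consent and first dose | Report | Not reportable (10.1; SAP 10.12.1) |
| Within 4 weeks after the last visit, patient side | Report once known | Patient not asked for it (10.2, exit instruction) |
| Within 4 weeks after the last visit, Investigator side | Report once known | Outside the notification request (10.2, closing part) |
| More than 4 weeks after the last visit | Outside the window | Not requested; no conflict |

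The first row is a direct contradiction. The second and third rows overlap the window because the exit instruction runs from the last visit and the notification rule from the end of participation. Neither says that it begins after week 4.

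**Step 2. Look for another route of detection after Day 28.** The 24-hour duty starts when the site learns of an event. Sections 10.1 and 10.2 require follow-up of unresolved AEs and SAEs, and Section 10.4 requires follow-up of a known pregnancy. These concern events already known and are not a systematic search for new SAEs.

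**Step 3. Check whether a precedence rule settles it.** Section 14.8 lets the SAP prevail on planned statistical analysis. That does not help, because SAP Section 10.12.1 repeats the pre-dose restriction and also refers to Protocol Section 10.2 for SAE reporting.

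**Step 4. Count days.** Inputs: screening up to 14 days; on-study time at least 60 days (Section 9.1.1) or about 8 weeks, 8 × 7 = 56 days (synopsis); post-visit window 4 × 7 = 28 days. Screening and run-in Day 1 may be one visit (Sections 9.1.1 and 12.2), so the pre-dose interval runs from about 0 to 14 days.

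Share under a narrower rule = (pre-dose + 28) / (pre-dose + on-study + 28).

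- Pre-dose 14, on-study 60: 42/102 = 41%
- Pre-dose 14, on-study 56: 42/98 = 43%
- Pre-dose 0, on-study 60: 28/88 = 32%
- Pre-dose 0, on-study 56: 28/84 = 33%

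A longer run-in lowers all four. The 28 days without scheduled contact are the same in every scenario.

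**The case against.** The strongest reply is that the text can be read as two tiers: all causes for 4 weeks, related events only after that. The notification rule's open-ended time span fits this reading, and it is probably what was meant. However, neither related-only sentence states the boundary, and a site has to work from what is written. The reading supports clarification; it does not make it unnecessary.

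Second, the lost information may be small. Mean half-life is 1.6 to 1.8 hours (Section 7.4.1), so one day after the last dose is already about 24/1.8 = 13 mean half-lives, though Section 7.4.3 reports more drug-related AEs in slow acetylators and Section 7.4.1 a longer half-life. Patients given amifampridine first stop it around Day 14. An SAE late in the window that no physician suspects is unlikely to change the safety profile much. This stands as a limit on the consequence. It does not explain why the plan sets a window and then does not ask for the events in it.

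Third, before first dose the drug cannot be the cause, and Table 6 classes events without exposure as not related. Treatment-emergent tables start at randomization (SAP Section 10.12.1). The pre-dose conflict is therefore mainly one of wording.

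A reader might go further and infer three things that the documents do not support.

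- **That patients are told not to report unrelated events.** They are told what to report; nothing is forbidden, and a physician's belief that an event might be related is a low bar.
- **That patient reports are the only possible source.** The site may learn of events through ordinary care or through follow-up of open AEs.
- **That the trial would present its post-treatment SAEs as completely collected.** No section makes that claim. SAP Section 10.12 says only that observed safety data will be listed.

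**Conclusion.** The rules conflict as written, and following them can leave SAE collection incomplete. The part that matters is the 28 days after the last visit, when SAEs not presumed related are within the window, are not asked for, and have no scheduled contact to bring them to light. The pre-dose conflict, lasting 0 to 14 days before exposure, is secondary.

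It would be too strong to conclude that SAEs will be missed. Any SAE that reaches the site in the window must still be reported whatever its cause, so the weakness lies in finding events, not in the duty to report them. The day shares of 32% to 43% describe calendar time, not events or risk. The upper values assume a full 14-day screening and combine two different restrictions, and all of them fall with a longer run-in. The number of SAEs affected cannot be derived from the documents.

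The conclusion assumes that no site instruction outside the protocol and SAP supplies the missing boundary. No efficacy result depends on it.

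**What to change.** Needed, wording only:

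1. In Protocol Section 10.2, change the exit instruction so that patients are asked for any SAE, whatever its cause, up to 4 weeks after the last visit, and after that only for SAEs thought related to study treatment.
2. In the closing part of Section 10.2, state that the Investigator's related-only notification applies once those 4 weeks have passed. Without this, correcting the patient instruction alone leaves a conflict.
3. Align the pre-dose sentence in Protocol Section 10.1 and SAP Section 10.12.1 with Section 10.2 and Table 1, footnote h.

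Optional: add to Table 1 one telephone or video contact at the end of the 4 weeks for everyone who took amifampridine, including run-in patients who were not randomized. The protocol already uses such contacts during titration. The contradiction does not itself require this step, but it would give the window a planned means of finding events.

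The cost is a protocol and SAP text change and, if the contact is added, one short call per exposed patient (about 12 randomized plus those who stop in run-in). No visit or procedure is added.

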10.3 Safety Blood Collection

Patients who experience a serious or severe AE should have, at the discretion of the Investigator, a blood sample drawn for safety labs as soon as possible after the AE began.

Additional blood sampling may be performed at any time during the study if warranted to monitor patient safety.

10.4 Pregnancy

Pregnancy in a patient or partner should be reported within 24 hours of the site becoming aware of the pregnancy by fax or email of the Pregnancy Reporting Form in the study reference materials to Catalyst. In addition, pregnancy in a patient is also reported on the End of Study CRF. The Investigator must make every effort to follow the patient through resolution of the pregnancy (delivery or termination) and to report the resolution on the follow-up form (Pregnancy Reporting Form: Additional Information in the study reference materials). In the event of pregnancy in the partner of a study patient, the Investigator should make every reasonable attempt to obtain the woman's consent for release of protected health information.

10.5 Urgent Safety Measures

The regulations governing clinical trials state that the sponsor and Investigator are required to take appropriate urgent safety measures to protect subjects against any immediate hazards that may affect the safety of subjects, and that the appropriate regulatory bodies should be notified according to their respective regulations. According to the European Union (EU) Clinical Trial Directive 2001/20/EC, "...in the light of the circumstances, notably the occurrence of any new event relating to the conduct of the trial or the development of the investigational medicinal product where that new event is likely to affect the safety of the subjects, the sponsor and the Investigator shall take appropriate urgent safety measures to protect the subjects against any immediate hazard. The sponsor shall forthwith inform the competent authorities of those new events and the measures taken and shall ensure that the IEC is notified at the same time. The reporting period for urgent safety measures is the period from the time of signing of the ICF through the completion of the last study visit. Investigators are required to report any urgent safety measures to the Sponsor or designee within 24 hours.

Page 47

Examples of situations that may require urgent safety measures include discovery of the following:

- An immediate need to revise IP administration (i.e. modified dose amount or frequency not defined in protocol).
- Lack of study scientific value, or detrimental study conduct or management.
- Discovery that the quality or safety of IP does not meet established safety requirements.

11 APPROPRIATENESS OF MEASUREMENTS

The measures of safety used in this study are routine clinical and laboratory procedures. The efficacy measures use a variety of approaches to evaluate changes in neuromuscular function and muscle strength. These standardized tests have been previously used for determination of response to the apeutic intervention in patients with SMA and thus are relevant for use in this study in ambulatory patients with SMA.

12 STUDY PROCEDURES

12.1 Screening Visit

An ICF must be signed and dated by the patient and parents for patients with age < 18 years, the Investigator or designee, and witness (if required) before any study-related procedures are performed. Refer to Section 9.4 for prohibited medications.

After patients have signed an ICF, they will be screened for enrollment into the study. The study activities listed below will be performed during the 14 days that constitute the Screening visit.

- Informed Consent;
- Inclusion/Exclusion criteria;
- Demographics (sex, race, ethnic origin, age);
- Medical history, including allergy history;
- Standard resting 12-lead ECG;
- Complete physical examination including weight and height;
- Vital signs (seated position), including SBP, DBP, heart rate, respiration, and body temperature;
- Clinical laboratory tests including hematology, chemistry, and urinalysis;
- Serum pregnancy test in females of childbearing potential only;
- HFSME;
- Walk 30 meters;
- SAEs;
- Concomitant medications.

12.2 Open-label Run-in

Amifampridine dose will be titrated upward every 3 to 4 days, starting at 15 mg/day, at the discretion of the Investigator. Patients will either visit or have telephone/video contact with the site for each dose titration and at least one in-person site assessment at Week 3 of the Run-in period (Table 1). When the Investigator determines that the patient has reached the maximal tolerable dose, the patient should demonstrate they can remain on a stable dose and frequency for at least an additional 7 days. The Open-label Run-in period may be extended if additional time is needed for dose titration. At the end of this period, patients must show a ≥3-point improvement in HFMSE from start of Run-in, to be eligible for randomization (Day 0).

Patients should be given a Drug Dosing Diary to record each dose of their open-label medication and instructions on how to complete the form.

Additional visits are allowed as necessary. Screening visit and start of Run-in (Day 1) may be combined into a single visit.

12.3 Period 1

12.3.1 Day 0

Patients who are deemed eligible for continuation will have the assessments/procedures listed below completed on Day 0 after taking a supervised dose of their medication for that day during the clinic visit, so that the assessments can occur in the prescribed relation to the time of medication administration.

- Confirmation of Inclusion/Exclusion criteria;
- Assessment of AEs/SAEs;
- Complete physical exam with weight;
- Vital signs (seated position), including SBP, DBP, heart rate, respiration, and body temperature;
- Standard resting 12-lead ECG;
- Clinical laboratory tests including hematology, chemistry, and urinalysis;
- Urine pregnancy test in females of childbearing potential only;
- Concomitant medications;
- Collect patient Drug Dosing Diary and perform IP accountability of open-label medication;
- Efficacy assessments following in-clinic dose of open-label medication as listed below:

Order of Assessment at Each Study Visit (when applicable)	Start Time After Dose (+ 10 minutes unless otherwise specified)
HFSME	45 minutes
6-minute walk test	After HFSME
Time to rise from floor	After 6-minute walk
Time to rise from chair	After rise from floor
Time to climb 4 stairs	After rise from chair
Time to walk 10 meters	After climb stairs
Quality of Life Assessment	After 10-meters walk

- INQoL for neuromuscular disease or the PEDSQLTM assessments will be completed for adult or pediatric patients, respectively after the six other assessments have been made.
- Randomization to Treatment Sequence

All open-label IP should be collected from the patient. The Investigator will dispense bottles containing amifampridine or placebo tablets, depending on the patient's randomization assignment, for daily outpatient administration for 14 days (Days 1-14), starting after completion of all assessments on Day 0.

Patients should be given a Drug Dosing Diary to record each dose of their double-blind medication and instructions on how to complete the form.

Patients continue administration of blinded study medication (amifampridine or placebo) until the Day 14 visit.

